Study Protocol and Statistical Analysis Plan Cover sheet:

Title: Epidermal Permeability Barrier Function and Stratum Corneum Hydration of Rosacea Following Application of Ivermectin

NCT Number: NCT04275999

Date of document: 02/19/2021

Title: Epidermal Permeability Barrier Function and Stratum Corneum Hydration of Rosacea Following Application of Ivermectin

Principle Investigator: [name], PhD

Sponsor or funding source: Galderma

Study Rationale:

Facial erythema is the hallmark of rosacea and the mandatory criterion for its diagnosis.(1) It is estimated that rosacea-related erythema affects more than 40 million people worldwide. The repair and maintenance of the epidermal barrier are critically important in the treatment of rosacea. Rosacea lesions can have a defective barrier, characterized by elevated transepidermal water loss (TEWL) rates and reduced levels of stratum corneum (SC) hydration.(2) The skin barrier function is a critical factor for assessing the severity of rosacea. The precise mechanisms underlying the relationship between rosacea and skin barrier function are not yet known. Some argue that impaired skin barrier function is a consequence of inflammation and continuous stimulation, while others attribute it to infection with follicle mites.(3)

Ivermectin possesses anti-inflammatory by effecting cytokines and neutrophils, and anti-parasitic properties by effecting *Demodex* mites. (4, 5) Ivermectin offers a potential treatment option in maintenance therapy. (6) Recent attention has been directed toward the maintenance and prevention of relapse of rosacea. Treatment with ivermectin may decrease follicle mites, thereby decreasing rosacea flares, improving epidermal barrier dysfunction, reduces TEWL, and improves SC hydration.(7) However, topical application of medications can be complicated, time-consuming, and often frustrating. Poor adherence to therapy can lead to treatment failure and poor health outcomes.(8, 9)

Frequent office visits improve adherence, but are rarely feasible in everyday practice.(10, 11) Reminders are helpful for patients who are strongly motivated to take the medication but sometimes forget. For the majority of patients, who have not completely bought into the regimen, a subtler approach appears better. This approach aims at building intrinsic motivation, trust, feelings of being cared for, and accountability through frequent contact. In a pilot study of teenagers with acne, sending weekly surveys querying subjects about perceived burden of treatment, perceived usefulness of the medication, current disease severity, and side effects raised mean adherence to 89%, compared to 33% in the control group.(12) The present study aims to validate a very similar tool for patients at risk for low adherence to ivermectin.

Another limitation to improving patients' adherence to topical treatments is that there has not been a practical way to give patients feedback on the state of their skin barrier. Measuring TEWL rates and SC hydration levels could be a valuable tool to give patients this feedback. We propose to test whether we can improve patients' use of topical ivermectin in subjects with rosacea by using a portable hydration measurement device that simultaneously measures both the TEWL rates and SC hydration levels in a study in which we would objectively measuring adherence to daily ivermectin.(13)

Our primary hypothesis is that weekly digital interactions and routine measurement of TEWL rates and SC hydration levels will promote patient adherence to maintenance ivermectin therapy and prevent disease relapse. The project will consist of a trial in which thirty subjects with rosacea receive ivermectin therapy and are randomized to receive either no intervention, a

weekly digital survey to assess patient's attitudes towards ivermectin therapy, or a portal hydration measurement device that measures TEWL rates and SC hydration levels. We will measure adherence objectively in all groups with electronic monitors attached to the containers of the ivermectin, which all subjects will be told to use daily for maintenance therapy. Additionally, the hydration measurement device can transmit data to an Internet server via a smartphone using Bluetooth technology, thereby allowing providers to monitor a patient's TEWL rate and SC levels.

Objectives:

- Determine the effect of the portable hydration measurement device on treatment adherence to daily ivermectin therapy
- Determine the effect of weekly digital survey on treatment adherence to daily ivermectin therapy
- Determine the effect of daily ivermectin therapy on TEWL rate, SC levels, and rosacea treatment outcomes

Methods and Measures:

Study Design:

Adult subjects will be offered an opportunity to participate in the study. Subjects will either have a diagnosis of rosacea. A total of 30 subjects will be enrolled. After consent and basic demographics, a study team member will use the GPSkin Barrier® to measure the baseline moisture level of the face of all subjects. Subjects will also fill out questionnaires pertaining to quality of life, accountability, patient-physician relationship, and severity of rosacea.

Subjects will be randomized into one of three arms: the control group (n= 10), the digital interaction group (n=10), or the GPSkin group (n=10). All patients will receive ivermectin equipped with an electronic monitor to measure adherence for daily treatment of rosacea. The digital interaction group will receive a survey by email each week asking about their use ivermectin generated by Causa Research. The patients in the GPSkin group will receive the GPSkin Barrier® to measure their moisture level of their face daily. Subjects will be instructed to use the ivermectin once daily. Subjects will return at 3 Months. At this visit, the data from the electronic adherence monitoring will be downloaded, the ivermectin will be weighed, and the patient will fill out the same questionnaires (quality of life, accountability, patient-physician relationship, and severity of rosacea). The intervention subjects will be evaluated on their use of the GPSkin Barrier® to measure their stratum corneum hydration. Participants not randomized to the email intervention group will receive an accountability questionnaire at the beginning and end of the study.

Setting

The study will be conducted at Department of Dermatology at Wake Forest School of Medicine. Data will also be analyzed at Department of Dermatology at Wake Forest School of Medicine.

Subject Selection

Inclusion Criteria

- Subject is 18 years of age or older.
- Subject has a working knowledge of English.
- Subject with a diagnosis of Rosacea
- Subjects without a known allergy to ivermectin
- Subjects with access to a smart phone

Exclusion Criteria

- Subjects under 18 years of age.
- Subject does not have a working knowledge of English.
- Subject with a diagnosed skin condition other than rosacea
- Subjects with a known allergy to ivermectin
- Subjects without access to a smart phone

Intervention and Interactions

Patients will be recruited from the Dermatology Clinic or from the Dermatology Clinic Database. Team members can recruit in-person with patients in the Dermatology Clinic, or by calling patients with a diagnosis of Rosacea (ICD 10: L71.9). Patients will then be brought to the Center for Dermatology Research for their initial screening visit. Demographic data collected from the patient includes sex, age, and ethnicity.

Outcome Measure

Outcomes include adherence (as measured by electronic monitoring), weight of the ivermectin, rosacea severity, quality of life, reporting of adverse effects, accountability questionnaire, and use of the GPSkin Barrier® in the GPSkin group. Data from the clinical study will be analyzed by a biostatistics software. Correlation between demographics will be measured.

Analytical Plan

Data will be analyzed using descriptive statistics on a biostatistics software.

Human Subjects Protection

Subject Recruitment Methods

Subjects who meet the inclusion and exclusion eligibility criteria will be able to participate in the study. Subjects are recruited at a clinic in the Department of Dermatology at Wake Forest School of Medicine or through the Department of Dermatology Database.

Informed Consent

Informed consent will be acquired for this study. The risk of harm or discomfort is not expected to be more than a daily life or routine physical or psychological exam or test. Rights and welfare of subjects will be protected through the use of measures to maintain the confidentiality of study information. No identifying information will be taken from the patient. The only information taken from the patient includes age, gender, ethnicity, location of the skin lesion, and email addresses. The information collected for this research study includes quality of

life, accountability, and severity of rosacea information. Results of the study will be published or presented in lieu of providing individual subjects additional information regarding the study.

Confidentiality and Privacy

Confidentiality will be protected by collecting information needed to assess study outcomes, minimizing to the fullest extent possible the collection of any information that could directly identify subjects, and maintaining all study information in a secure manner. To help ensure subject privacy and confidentiality, no subject identifiers will be used. The results of the survey will be presented as an anonymous data set. Data access will be limited to study staff. Data will be kept locked and secured, with computer data password protection. No references to any individual participant will appear in reports, presentations, or publications that may arise from the study.

Data and Safety Monitoring

The principal investigator will be responsible for monitoring data and safety of subjects. The principal investigator will be assisted by other members of study staff.

Report of Unanticipated Problems, Adverse Events, or Deviations

All unanticipated problems, serious or unexpected adverse events, deviations or protocol amendments will be reported by the principle investigator or designated member of the research team to IRB or appropriate government agency if appropriate.

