Subtype 3: Phymatous	 Absent	 Mild	 Moderate	 Severe
Subtype 4: Ocular	 Absent	 Mild	 Moderate	 Severe

Patient's global assessment ☐ Clear ☐ Mild ☐ Moderate ☐ Severe

Initial symptoms occurred: _____

Treatment prescribed: _____

Comments: _____

Physician: _____

National Rosacea Society • [name] • [name]

Based on "Standard grading system for rosacea: Report of the National Rosacea Society Expert Committee on the Classification and Staging of Rosacea." J Am Acad Dermatol 2004;51:951-12.
© 2004

Investigator Global Assessment

Scores		
0	Clear	No inflammatory lesions present, no erythema
1	Almost Clear	Very few small papules/pustules present, very mild erythema
2	Mild	Few small papules/pustules, mild erythema
3	Moderate	Several small or large papules/pustules, moderate erythema
4	Severe	Numerous small and/or large papules/pustules, severe erythema

Patient Self-Assessment

Scores		
0	Clear	No Redness
1	Almost Clear	Very Mild Redness
2	Mild	Mild Redness
3	Moderate	Moderate Redness
4	Severe	Severe Redness

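### Relapse prevention is half of the primary hypothesis, but entry does not require remission, relapse is not an outcome, and severity is recorded only at baseline and 3 months

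*Combined protocol and SAP*

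**What the plan says.** The document is a combined protocol and SAP.

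- **Hypothesis.** The Study Rationale states, as the primary hypothesis, that weekly digital contact and routine barrier measurement "will promote patient adherence to maintenance ivermectin therapy and prevent disease relapse". It describes the ivermectin as a product "which all subjects will be told to use daily for maintenance therapy".
- **Study Design** describes the same product differently: "All patients will receive ivermectin equipped with an electronic monitor to measure adherence for daily treatment of rosacea".
- **Entry.** The disease criterion is "Subject with a diagnosis of Rosacea". The remaining criteria cover age, English, ivermectin allergy, smartphone access and other skin conditions. Recruitment is in clinic or by "calling patients with a diagnosis of Rosacea (ICD 10: L71.9").
- **Objectives.** Two concern adherence. The third is "Determine the effect of daily ivermectin therapy on TEWL rate, SC levels, and rosacea treatment outcomes". None names relapse.
- **Outcomes.** "Outcomes include adherence (as measured by electronic monitoring), weight of the ivermectin, rosacea severity, quality of life, reporting of adverse effects", followed by the accountability questionnaire and device use. Relapse is not in the list and is defined nowhere.
- **Schedule.** Subjects complete severity questionnaires at baseline and again at the only return visit, at 3 months.
- **Analysis.** The Analytical Plan offers descriptive statistics only.

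**The concern.** A claim about preventing relapse needs three things: subjects whose disease is under control, a rule for when control has been lost, and observation often enough to see it happen. The plan provides none of them for all arms.

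Subjects may enter with any degree of activity. Some would be trying to hold a good state and others to reach one. If the 3-month severity scores of the two kinds are pooled, a difference between arms could come from better response among those with active disease, less worsening among those already controlled, or a chance imbalance in the mix with 10 subjects per arm. The data would not separate these.

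At stake is what the report may say. With relapse in the primary hypothesis, a favourable severity difference invites the statement that the interventions prevented relapse, and an unfavourable one invites the opposite. A relapse definition chosen after the scores are seen would be post hoc.

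**Working it through.** **No stated figure to reproduce.** The plan gives no power, alpha, effect size or relapse rate. The only check available is the arm total, 10 + 10 + 10 = 30, which agrees with the stated enrolment.

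**Requirement against provision.**

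| Needed for a relapse claim | What the document provides |
|---|---|
| Controlled disease at entry | A diagnosis only (Inclusion Criteria); no score, remission or prior response required |
| One description of the therapy setting | Maintenance (Study Rationale) against treatment (Study Design) |
| A defined event | None. The Investigator Global Assessment (IGA) in Appendix IV has a level 1, "Very few small papules/pustules present, very mild erythema", but no level or change is named as relapse |
| Repeated scoring in every arm | Baseline and 3 months only |
| An at-risk group in the analysis | None |

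The weekly email survey (Appendix III) does not fill the fourth row. It goes to the digital interaction arm alone and asks whether the medication seems to be helping, so it is neither a severity score nor comparable between arms.

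**Illustration of size.** Let *m* be the number per arm who are clear or almost clear at entry. The document does not restrict *m*, so the whole range 0 to 10 is open. Equal *m* in the two compared arms is assumed.

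- Exact upper 95% limit for the relapse proportion when 0 of *m* relapse: 1 − 0.025^(1/*m*).
- Smallest attainable two-sided Fisher p-value (all relapse in one arm, none in the other): 2 / C(2*m*, *m*).
- Fisher power at two-sided 0.05 for **assumed** relapse rates of 60% versus 20%, summed over all possible outcome tables.

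| *m* per arm | Upper limit for 0/*m* | Smallest p | Power, 60% v 20% |
|---|---|---|---|
| 0 | not estimable | none | none |
| 1 | 97.5% | 2/2 = 1.00 | 0% |
| 3 | 71% | 2/20 = 0.10 | 0% |
| 5 | 52% | 2/252 = 0.008 | 14% |
| 8 | 37% | 2/12,870 = 0.0002 | 24% |
| 10 | 31% | 2/184,756 = 0.00001 | 25% |

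With all 10 per arm at risk, other assumed pairs give 6% (30% v 10%), 6% (40% v 20%), 9% (50% v 25%), 12% (60% v 30%) and 43% (70% v 20%). The mismatch in the first table does not depend on any of these rates.

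**The case against.** The strongest reply is that this is a small descriptive study. The Analytical Plan sets no test and no success criterion, and the Objectives do not promise relapse prevention, so one clause in a rationale does little harm. This stands in part: nothing would be formally accepted or rejected. But the clause sits in what the document itself calls its primary hypothesis, and a small pilot is a reason to narrow the claim. A second reply is that severity can stand in for relapse. It could, given a prespecified at-risk group, a threshold and more than one follow-up score, and the document has none of these.

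Several stronger readings are tempting but unsupported:

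- *Only a subject clear at entry can relapse.* A subject with active disease could clear on treatment and worsen again within 3 months. The design would miss this because it has one follow-up score.
- *Active disease at entry means initial treatment.* Eligibility says nothing about prior treatment, so this cannot be inferred.
- *A particular share, such as 40–50%, starts in remission.* The document gives no basis for any share, hence the full range above.
- *The IGA is already collected at both visits.* It is printed in Appendix IV, but Study Design describes severity only through questionnaires that the subject completes. No investigator rating is scheduled.
- *A 3-month IGA cut-off would repair the relapse endpoint.* It would still be a single follow-up score and would miss anything that resolved earlier.

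**Conclusion.** The concern holds as a mismatch between the primary hypothesis and the design. As written, the trial cannot show that the interventions prevent relapse, and a 3-month severity difference should not be reported as if it did. This rests on the text alone: the entry criteria, objectives, outcome list, visit schedule and analysis plan.

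The size can only be illustrated, because the entry mix and relapse rates are not given. Across 0 to 10 subjects at risk per arm, the information on relapse runs from none to roughly 6–43% power under the assumed rates. At the upper end the limit is mainly the arm size of 10 rather than the missing remission criterion.

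A reader might infer that the whole primary hypothesis fails. It does not on this ground: adherence is measured electronically in all arms, and that half is untouched. A between-arm comparison of severity at 3 months is also legitimate as such; it is just not a measure of relapse.

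**What to change.** 1. Delete the relapse clause from the primary hypothesis, leaving adherence as the sole primary question.
2. Reconcile the maintenance wording in the Study Rationale with the treatment wording in Study Design.
3. Add a secondary aim: the between-arm difference in rosacea severity at 3 months, adjusted for baseline, on one named Appendix IV scale. State it in the Analytical Plan as an estimate with a confidence interval.
4. Name the scale. The Patient Self-Assessment (0–4) fits the subject-completed questionnaires already scheduled at both visits, though its levels describe redness only. The IGA also covers papules and pustules, but should be used only if the protocol states that it is rated at both visits.
5. Show worsening among subjects clear or almost clear at baseline descriptively only, with the number at risk in each arm, and state that it is not evidence of relapse prevention.

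Make these changes before severity is examined by arm. With the Self-Assessment the cost is wording alone; with the IGA it is a scheduled investigator rating at each of the two visits. No added visit or subject is needed. The real price is that the trial gives up its relapse claim.

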Appendix I: Demographic Questions for Patients

1. What is your gender?
 - Male
 - Female
 - Other
2. What is your ethnicity?
 - Caucasian
 - African American
 - Asian
 - Native American
 - Other
3. What is your age?
 - Open ended question.
4. Do you regularly use a moisturizer on your skin?
 - Yes
 - No
 - Intermittently
5. If you use a moisturizer, what is the name of the moisturizer?
 - Open ended question.

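### Objective 3 asks for the effect of ivermectin, but every subject receives it and no 3-month barrier reading is listed for all arms, so the trial can at most describe change from baseline

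*Combined protocol and SAP*

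**What the plan says.** Under Objectives, the third item is to "Determine the effect of daily ivermectin therapy on TEWL rate, SC levels, and rosacea treatment outcomes". Study Design gives the arms as "the control group (n= 10), the digital interaction group (n=10), or the GPSkin group (n=10"), and says that "All patients will receive ivermectin equipped with an electronic monitor to measure adherence for daily treatment of rosacea". The Study Rationale shows that the control arm lacks only the adherence intervention and is still on ivermectin.

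For measurement, Study Design states that "After consent and basic demographics, a study team member will use the GPSkin Barrier" on all subjects at baseline. At the single return visit, at 3 months, the monitor data are downloaded, the ivermectin is weighed, and "the patient will fill out the same questionnaires (quality of life, accountability, patient-physician relationship, and severity of rosacea"). The only mention of the device at that point is that the intervention subjects' use of it will be evaluated. The Outcome Measure section lists adherence, ivermectin weight, rosacea severity, quality of life, adverse effects, the accountability questionnaire and device use in the GPSkin group. TEWL and hydration are not on the list.

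The demographic form (Appendix I) asks "Do you regularly use a moisturizer on your skin" and then for the product name. The Analytical Plan specifies descriptive statistics only.

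**The concern.** The objective is worded causally, but the design randomises something else. Change over 3 months on ivermectin combines any drug effect with the natural course of rosacea, season, regression to the mean, changes in other skin care and the study interventions themselves. With nobody off the drug, no analysis of these data can take that mixture apart. The study title also puts barrier function and hydration after ivermectin at the centre, so a before-after difference could easily be read as a drug effect.

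Two gaps in data collection add to this. If no reading is taken at 3 months in the control and survey arms, the barrier part of the objective has no paired data there at all. And moisturizer, which can itself alter hydration and TEWL, is recorded once, so a change in its use during follow-up would go unseen.

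**Working it through.** **1. What contrast exists.** "A total of 30 subjects will be enrolled"; 10 + 10 + 10 = 30, so the arm sizes agree with the total. All 30 receive ivermectin, so the number without it is 30 − 30 = 0. There is no vehicle, untreated or delayed-start group. What remains for objective 3 is baseline against 3 months within subjects.

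**2. What data exist for that contrast.**

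| Item | At entry | At 3 months |
|---|---|---|
| Staff GPSkin reading, all subjects | Yes | Not listed |
| Rosacea severity | Yes | Yes |
| Moisturizer use and product (Appendix I, items 4-5) | Yes, on the demographic form | Not listed; the weekly survey (Appendix III) has no such item either |

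So a before-after change is specified for severity in all arms. For TEWL and hydration, follow-up readings can be inferred only in the GPSkin arm (n = 10), from the subjects' own daily use of the device.

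**3. How large a spurious change could be.** The plan gives no SD, correlation or entry severity, so this is an illustration under stated assumptions. Everything is in SDs of the measure, with equal variance at both times and all 30 subjects returning.

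- Expected change with no drug effect, when subjects enter z SD worse than the population mean: z × (1 − r), where r is the baseline-to-3-month correlation.
- SD of change: √(2(1 − r)).
- 95% CI half-width for mean change: t(0.975, 29)/√30 × √(2(1 − r)) = 0.373 × √(2(1 − r)).

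With z = 1:

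- r = 0.5: artefact 1 × 0.5 = 0.50; half-width 0.373 × √1.0 = 0.37.
- r = 0.8: artefact 1 × 0.2 = 0.20; half-width 0.373 × √0.4 = 0.24.

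The artefact exceeds the half-width when √(1 − r) > 0.373 × √2 = 0.528, that is, for r below about 0.72. With z = 0.5 the condition becomes √(1 − r) > 1.056, which no r between 0 and 1 meets.

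**The case against.** **The plan is descriptive and the primary hypothesis is about adherence.** This is fair and limits the consequences. Objectives 1 and 2 are randomised comparisons of adherence, and a descriptive before-after summary is legitimate. But a descriptive analysis cannot answer an objective that asks for an effect, which is a reason to change the wording.

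**The arms may differ in adherence, so randomisation might inform the drug effect indirectly.** No such analysis is specified, and it would be weak. Suppose the survey arm reached the adherence contrast that the Study Rationale quotes from an acne pilot, 89% − 33% = 56 points, and benefit were proportional to adherence (both assumptions). A true drug effect of 1 SD would then appear as 0.56 SD between two arms of 10. Power at two-sided 5% (normal approximation) would be about 24%.

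**Regression to the mean may be small here.** This stands. Eligibility requires a rosacea diagnosis, with no threshold for severity, TEWL or hydration, and recruitment includes calls to patients in a database. Nothing in the documents supports z = 1.

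**The moisturizer point is secondary.** This also stands. A reader might infer that GPSkin subjects, seeing a daily reading, will moisturize more, and that this would be counted as adherence or would bias a comparison between arms. The documents do not support that. Adherence is measured by monitors on the ivermectin containers and by weighing. The behaviour itself is conjecture, and if it occurred it would arguably be part of the assigned device's effect. No between-arm hydration comparison is planned.

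**Conclusion.** The concern holds in limited form. Objective 3 cannot be met as worded, because no subject is without ivermectin; this follows from the design alone and rests on no assumed figure. The TEWL and hydration part has a further gap, since the plan does not list a follow-up reading in all arms or name these measures as outcomes. The entry-only moisturizer question is a lesser weakness: repeating it would aid interpretation but would not make the comparison causal.

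A reader might go further and infer that regression to the mean alone would produce a significant improvement. The documents do not support this. No significance test is planned, entry severity is unknown, and even at z = 1 the expected artefact is above the half-width at r = 0.5 (0.50 against 0.37) but below it at r = 0.8 (0.20 against 0.24). The figures show only that the artefact could be of a size that matters. Nor does the point undermine the adherence comparisons.

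**What to change.** - Reword objective 3 along these lines: *Describe change from baseline to 3 months in TEWL, SC hydration and rosacea severity during ivermectin use, all arms pooled.* Report paired mean change with a 95% CI and make no causal claim.
- State in Study Design that the staff GPSkin reading is repeated in all subjects at the existing 3-month visit, and add TEWL and SC hydration to the Outcome Measure list.
- Repeat Appendix I items 4-5 at 3 months in all arms, and report change in moisturizer use by arm as descriptive context. Do not present the subset with unchanged moisturizer use as an adjusted estimate: it would condition on a variable observed after randomisation, in at most 30 subjects.

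The cost is a softer claim about ivermectin, one short device reading per subject and two questions, all at a visit already planned.

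### In the GPSkin arm, staff take the baseline barrier reading and subjects take the later ones, and the probe site on the face is neither fixed nor recorded

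*Combined protocol and SAP*

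**What the plan says.** Study Design (under Methods and Measures) has two instructions on where and by whom the device is used. At baseline, "a study team member will use the GPSkin Barrier® to measure the baseline moisture level of the face of all subjects". Afterwards, "The patients in the GPSkin group will receive the GPSkin Barrier® to measure their moisture level of their face daily". The operator therefore changes from staff to subject, and the site is described no more closely than the face on either occasion.

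The third objective depends on these readings: "Determine the effect of daily ivermectin therapy on TEWL rate, SC levels, and rosacea treatment outcomes". The Study Rationale gives the reason why site could matter: "Rosacea lesions can have a defective barrier, characterized by elevated transepidermal water loss (TEWL) rates and reduced levels of stratum corneum (SC) hydration".

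At 3 months, "the data from the electronic adherence monitoring will be downloaded, the ivermectin will be weighed, and the patient will fill out the same questionnaires". Subjects' use of the device is also evaluated then, but no staff reading with it is listed for any arm. The control and digital interaction arms (20 of 30 subjects) have no stated reading after baseline.

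The nearest thing to a site record is in Informed Consent, which lists "age, gender, ethnicity, location of the skin lesion, and email addresses" among the items collected. The Rosacea Clinical Scorecard in Appendix IV also has a line for peripheral locations. Both describe where the disease is, not where the probe was placed.

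**The concern.** If lesional skin reads differently from uninvolved skin, a change from baseline can be interpreted only when both readings come from the same place. As written, staff may read an involved cheek and the subject may then read an uninvolved forehead at home, and both comply with the plan. That subject would appear to improve with no change in the barrier.

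The design has no way to absorb this. All arms receive ivermectin and only the GPSkin arm has follow-up readings, so the barrier question rests on an uncontrolled before-after comparison in at most 10 people. The operator changes straight after baseline, so any difference in where staff and subjects tend to place the probe is confounded with time on treatment. A site that was never recorded cannot be recovered at analysis. The same readings are the feedback given to subjects, so a subject who moves the probe may see swings that are not changes in the skin.

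**Working it through.** **1. What can be reproduced.** The arm sizes add up (10 + 10 + 10 = 30). The documents give no barrier values, SD, lesional difference or power calculation, so there is no stated figure to reproduce. All magnitudes below rest on assumed inputs.

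**2. Noise when the site is chosen afresh each time.** Let s_w be the SD of repeat readings at one site and s_s the SD between sites within a face.

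- Fixed site: Var(change) = 2·s_w².
- Free site: Var(change) = 2·(s_w² + s_s²).
- Ratio: 1 + (s_s/s_w)².

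For an assumed s_s/s_w of 0.5, the ratio is 1.25 and the standard error rises by √1.25 − 1 = 12%. For 1.0, the ratio is 2.0 and the rise is √2 − 1 = 41%.

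This leaves out variation between subjects in their true change, which also enters the standard error of a group mean. If that variance equals 2·s_w² (a further assumption), the ratio becomes (4·s_w² + 2·s_s²)/(4·s_w²) = 1 + (s_s/s_w)²/2. That is 1.125 and 1.5 for the two cases, so the standard error rises by 6% and 22%.

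**3. Bias when the lesional share shifts.** Let d be the lesional-minus-uninvolved difference in units of the same-site SD of change. Let p0 and p1 be the shares of subjects read on lesional skin at baseline and at follow-up. With a true change of zero:

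- False mean change = (p1 − p0)·d.
- The SD of change is multiplied by √(1 + d²·[p0(1 − p0) + p1(1 − p1)]).

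The last two columns come from a simulation of 40,000 trials with 10 subjects each, using a two-sided paired t-test at 0.05. The plan specifies no such test; the columns only show how often a false change would look convincing.

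| d (assumed) | False mean change, 100% to 50% lesional | SD multiplier, 50% both times (no mean bias) | False-positive rate, 100% to 75% | False-positive rate, 100% to 50% |
|---|---|---|---|---|
| 0.5 | −0.25 SD | 1.06 | 0.06 | 0.11 |
| 1.0 | −0.50 SD | 1.22 | 0.09 | 0.24 |
| 1.5 | −0.75 SD | 1.46 | 0.14 | 0.39 |
| 2.0 | −1.00 SD | 1.73 | 0.16 | 0.50 |

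Example for d = 1: (0.5 − 1.0) × 1 = −0.50, and √(1 + 1 × [0.25 + 0.25]) = √1.5 = 1.22. For TEWL the negative sign reads as improvement. For hydration d has the opposite sign, and the false change again reads as improvement.

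**4. One fixed site.** With p0 = p1 = 1, the false mean change is (1 − 1)·d = 0 and the SD multiplier is 1. The simulated false-positive rate stays at about 0.05 for every d in the table.

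**The case against.** The strongest counter-argument is about reach, and most of it stands. A reader might infer that barrier change is compromised throughout the trial. It is not: only the 10 GPSkin subjects have home readings. The Outcome Measure section lists use of the device rather than TEWL or hydration values, the primary hypothesis concerns adherence and relapse, and adherence is measured by electronic monitor. The analysis is descriptive.

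A reader might also infer that any move of the probe will look like a treatment effect. The documents do not support that. A move gives a false change in one person; the group mean is biased only if the lesional share shifts systematically between staff and home readings. The Rationale says only that lesions can have a defective barrier and gives no size. Nor does it follow that the daily feedback must be erratic: a subject who habitually uses one spot gets consistent readings.

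It would also be too strong to say that lesion location goes unrecorded, since Informed Consent lists it. But a lesion-location field does not say where the probe was placed, so it does not answer the point.

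Finally, there is a larger gap beside this one: 20 subjects have no stated follow-up reading and no arm is untreated. Fixing the site will not by itself make the third objective answerable. That is true, but it does not excuse leaving the one available series without a defined site.

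**Conclusion.** The concern holds within limits. In the GPSkin arm, the baseline and later barrier readings differ in operator and may differ in site, and the documents neither fix nor record the site. The certain consequence is that change from baseline cannot be tied to one place on the skin. Noise follows if sites vary and differ in their readings; bias in the group mean needs, in addition, a systematic shift in the lesional share.

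The size is unknown. The standard-error increases of 12% to 41%, or 6% to 22% once between-subject variation is allowed for, and the false mean changes of 0.25 to 1.00 SD all depend on assumed ratios, differences and shares. They show that the problem could matter with 10 subjects, not that it will. The point bears on the third objective and on the feedback shown to subjects; it does not bear on the measurement of adherence. It is worth correcting because the change costs very little and the missing information cannot be reconstructed later.

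**What to change.** - Name in the protocol one anatomical site chosen by a rule that does not depend on current severity, for example a fixed point on a prespecified cheek. Choosing the worst point would invite regression to the mean, and there is no untreated arm to reveal it.
- Mark the site on a face diagram on the case report form, and record whether it is lesional at baseline.
- Instruct GPSkin subjects to take every home reading at that site.
- Use the same number of repeat readings for staff and home measurements, so that the two do not differ in precision.
- At the baseline visit, have each GPSkin subject take a reading at the marked site next to the staff reading. Home values can then be compared with a baseline from the same operator at the same site.

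The cost is one diagram, a sentence or two of instructions, and a minute or two more at the baseline visit. No extra visit is needed. The downside is that the result describes one site rather than the whole face.
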